Secondary outcomes will include family caregiver psychological distress symptoms measured with the PHQ-9 (depression),¹³ the GAD-7 (anxiety),¹⁴ and the PTSS (PTSD) at survey 3 (T3) (1 week post-randomization) and survey 4 (T4) (3 months). Systems outcomes will include post-randomization length of stay (LOS), use of aggressive care, discharge disposition, and hospice use.^{15,16} Clinicians will complete a brief palliative care attitudes scale at the time of consent.¹⁷ Aim 3's analysis of facilitators, barriers, and mechanisms will be based on transcribed semi-structured family and clinician interviews.

Study Overview Aim 1

The previous pilot showed compelling results, but also identified targets that could substantially improve app functionality. However, changes in an app's user interface or function, regardless of intention, can influence intervention delivery, data validity (e.g., ePRO system), as well as *usability*—the quality of the user's experience across domains of ease of use, efficiency, memorability, error rate, and

Protocol Version: 5.1 Dated: 13 June 2022 Page **7** of **42**

satisfaction.¹⁸⁻²⁰ Usability testing is a critical procedure because it can identify any problems proactively, using lessons learned to improve the software before its introduction in a clinical trial setting.^{1,19,21} Therefore, Aim 1, a cross-sectional refinement (*not* developmental) study involving 10-15 participants, will aim to improve efficiency, memorability, satisfaction, and overall decrease error rate. Participants eligible for this portion of the study will be healthy volunteers, specifically Duke employees, at least 18 years of age or older. Aim 1, completed concurrently with Aim 2 startup tasks, will target three key areas:

- Engagement and personalization: the study team will enable a 'Recommender System' to improve user experience including reminders and notifications, dashboard views unique to study role (e.g., CRC vs. clinical teams), enhanced visualization of needs data, single-click ICU team approval for study team members to approach families, and hovering box feedback in response to user-completed tasks.
- 2. Security: The Duke Health Technology Support team will ensure that the app system's security adheres to current standards throughout the course of the trial.
- 3. Interoperability: Standards will be used for EHR triggers with the assistance of DHTS ACE team programmers.

Aim 2

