Analyses similar to those conducted for the NEST (primary outcome analyses) above will be performed for the secondary family caregiver hypotheses involving PHQ-9, GAD-7, and PTSS scores at T3 and T4. While family caregivers will be interviewed at T4 regardless of patient survival, patient death could complicate the analyses in two key ways: (1) Presence of missing data due to family loss to follow up (i.e., non-random missing data) and (2) differences in family caregiver distress by patient survival status (i.e., heterogeneous effect). 35 To address the impact of patient death on outcomes, after first exploring reasons for and predictors of dropout, we will conduct a 2-step supplemental analysis. In Step 1, missing T4 data due to loss to follow up among family caregivers of survivors will be multiply imputed via SAS PROC MI. In Step 2, we will account for T4 outcomes that are missing due to death via composite endpoint and principal stratification methods to estimate the causal effects of the intervention in the presence of these unidentified outcomes and complicated missing data patterns. 36,37 For the key patient outcome, receipt of goal concordant care, we will use logistic regression models adjusting for the stratification variables, to examine if rates at T3 differ by treatment group. The key healthcare systems outcome, post-randomization hospital length of stay (LOS), provides a unique challenge due to the high expected mortality rate (40-50%). In addition to descriptive analyses, steps to examine treatment group LOS differences will include: (1) a proportional hazards model with death treated as a censoring event; (2) a chi-square test of mortality rate differences; and (3) a Brunner-Manzel rank test for the composite death-LOS outcome. This last step implements a recently developed methodology of a composite outcome that incorporates a numerical value for death (i.e., coded as the worst possible outcome or the longest possible stay) in the observed LOS distribution. 38,39

Aim 3

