As noted above, the DSMB will have the power to stop the trial at their discretion. The following is a possible stopping plan that could be adapted by the study DSMB for inclusion in the final DSMB Charter. Because this is an early phase trial, we will not have formal stopping rules based on efficacy or futility. Criteria for intervention discontinuation and stopping based on safety concerns will be determined in partnership with the study DSMB and codified in the DSMB charter before enrollment begins. We propose a strategy similar to that included in our past ICU-based RCTs that included family caregivers (e.g., R01 HL109823, PI: Cox). Three-month all-cause mortality will be the primary adverse event for the patients in study. We will examine the distribution of deaths by treatment arm three times during the trial: at 15, 25, and 50 deaths. At each of these interim looks, we will examine the distribution of deaths by study group and conducted either a non-parametric sign test or Wilcoxon signed-rank test to test the difference in median number of deaths between the arms. We will use Haybittle-Peto guidelines and stringently set the p-value at 0.001 to flag a significant difference between arms at each of these interim looks. If this difference is observed, this would then indicate a closer examination of related constructs, as well as proximate causes and circumstances surrounding death (e.g., timing and location of death, withdrawal of life support or not, comorbidities and illness severity, clinician expectations of survival). We will use the Patient-Centeredness of Care Scale to provide additional information on the alignment of patient treatment and values at the time of death. Although past end of life interventions have not increased mortality, it is possible that by better focusing decision makers' attention on patients' values, higher mortality could be observed in the intervention group by identifying patients for whom prolonged life support would be a state worse than death (Patrick DL, et al. Ann Int Med. 139:410-415, 2003; Holloway RG, et al. JAMA. 298:802-804, 2007). Yet if PCplanner—a non-directive intervention—led to more decisions to forego life support, this would be ethically permissible if the treatments received reflected patient-centered care as assessed by the PCCS (Institute of Medicine, 2001; Lin GA, et al. Arch Intern Med. 169:1551-1553, 2009; Holloway RG, et al. 2007). The primary adverse event for family caregivers will be symptoms of psychological distress as measured by the PHQ-9 and PTSS at T2 and T3. We propose to examine the distribution of scores by treatment arm three times during the trial: at 25, 75, and 100 caregivers. Using methods similar to those above, we could examine circumstances more closely as per DSMB guidelines.

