Appendix 5: Data Collection and Timing

A. Clinical / patient information Baseline General information Comorbidities Diagnoses APACHE II illness severity CPR information / baseline ICU type & admission source Across entire hospitalization CPR information / changes Palliative care consults Procedures and therapies Dates (mechanical ventilation, hospital, ICU)	T1 Baseline x (x)	T2 4 days post- randomization	T3 8 days post- randomization	T4 3 months post- randomization - (x)
General information Comorbidities Diagnoses APACHE II illness severity CPR information / baseline ICU type & admission source Across entire hospitalization CPR information / changes Palliative care consults Procedures and therapies		-		- - (x)
CPR information / changes Palliative care consults Procedures and therapies	(x) -	-	-	- (x)
Dates (mechanical ventilation, nospital, 100)	-	-	-	(x)
3 months 3 month status				(^)
Patient & family member information				
Contact info Gender DOB, race / ethnicity, gender, marital status, children Employment Relation to patient Social support Financial distress	х	-	-	-
NEST	Х	Х	Х	-
Goal concordant care	X	x	X	-
Quality of communication	Х	х	Х	-
Patient-Perceived Patient-Centeredness (PPPC) scale	-	-	X	-
PHQ-9	X	-	X	Х
GAD-7	Х	-	X	Х
PTSS	X	-	Х	Х
Relationship with physician	X	Х	Х	-
Physician discussed needs	Х	Х	Х	-
Readmitted?	-	-	-	Х
Clinician information				
Gender Age Race / ethnicity Rank Service	Study initiation	-	-	-
Physician responses				
I did family meeting	-	Х	Х	-

CPR: cardiopulmonary resuscitation; GAD-7: generalized anxiety disorder 7-item instrument; ICU: intensive care unit; NEST: Needs; Existential concerns; Symptoms; and Therapeutic interaction scale; PHQ-9: patient health questionnaire 9-item depression instrument; PTSS: post-traumatic stress scale

Protocol Version: 5.1 Dated: 13 June 2022 Page 40 of 42

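### The proposed safety looks use distress scores that are not collected at T2, and name mortality tests that do not fit two unpaired arms

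*Combined protocol and SAP*

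**What the plan says.** The text is in section 12 of the protocol, under the DSMB heading. It is introduced as provisional: "The following is a possible stopping plan that could be adapted by the study DSMB for inclusion in the final DSMB Charter". The charter itself is not among the documents.

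- **Patients.** Three-month all-cause death is the main patient safety event. Looks are set at 15, 25 and 50 deaths. At each, the team would have "conducted either a non-parametric sign test or Wilcoxon signed-rank test to test the difference in median number of deaths between the arms", with a p-value of 0.001 (sidedness not stated) as the flag. A flag leads to a closer look at the circumstances of the deaths.
- **Caregivers.** "The primary adverse event for family caregivers will be symptoms of psychological distress as measured by the PHQ-9 and PTSS at T2 and T3". Looks are set at 25, 75 and 100 caregivers. On method the text says only: "Using methods similar to those above, we could examine circumstances more closely as per DSMB guidelines".

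Three other places bear on this. The collection table ("Appendix 5: Data Collection and Timing") marks PHQ-9 and PTSS at T1, T3 and T4, with a dash at T2. Section 8 (Aim 2) refers to "secondary family caregiver hypotheses involving PHQ-9, GAD-7, and PTSS scores at T3 and T4". The same section lists "a chi-square test of mortality rate differences" among its final analyses.

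**The concern.** There are two separate faults in the same proposal.

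1. One of the two time points in the caregiver look has no data. T2 is the day-4 survey, and neither distress scale is scheduled there.
2. The mortality tests named are paired or one-sample tests. The trial randomizes individuals to two parallel arms of 75, stratified but not matched. At each look an arm has a single count of deaths, so there is no median number of deaths and no set of paired differences.

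If the wording passes into the charter unchanged, the caregiver look is half empty. The mortality look would offer one option that cannot be computed and another that works only under an unstated reading. That reading is less likely to flag an excess of deaths than an ordinary unpaired test at the same threshold.

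**Working it through.** **Time points.** The Appendix 5 rows, set beside the stopping plan:

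| Scale | T1 | T2 | T3 | T4 | Stopping plan asks for |
|---|---|---|---|---|---|
| PHQ-9 | yes | no | yes | yes | T2, T3 |
| PTSS | yes | no | yes | yes | T2, T3 |
| NEST (for comparison) | yes | yes | yes | no | not applicable |

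The NEST row shows that the table does distinguish T2 from the other surveys, so the dash is not a reading fault. No section schedules either distress scale at T2.

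**Can the named tests reach 0.001?** The plan gives no operating characteristics for these looks, so there is no stated figure to reproduce. Suppose the arms were paired within the 8 randomization strata (three two-level factors, section 3). The smallest two-sided p from either test is then 2 × (1/2)^8 = 0.0078, so 0.001 could never be reached. At least 11 pairs are needed: 2 × (1/2)^11 = 0.00098.

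**The binomial reading.** With 1:1 allocation and no effect, D deaths split as Binomial(D, 0.5). Two-sided p = 2 × P(X ≥ r). The smallest splits with p ≤ 0.001 are:

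- 15 deaths: 14:1, p = 0.00098
- 25 deaths: 21:4, p = 0.00091
- 50 deaths: 37:13, p = 0.00094

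A one-sided 0.001 rule gives the same splits.

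**Enrolment at each look.** Section 9 gives about 36 months for 150 patients: 150/36 = 4.17 per month. Section 8 expects 40-50% mortality; applying this at three months is an assumption. If deaths fall anywhere from day 0 to day 90, the lower limit is D/0.50 and the upper limit is D/0.40 + 3 × 4.17:

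- 15 deaths: 30 to 50 patients (15-25 per arm)
- 25 deaths: 50 to 75 (25-38 per arm)
- 50 deaths: 100 to 138 (50-69 per arm)

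**Fisher's exact test at the same threshold**, with equal numbers per arm:

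| Deaths | Smallest split flagged by Fisher | Binomial p for that split |
|---|---|---|
| 15 | 13:2 at 15-21 per arm; 14:1 from 22 | 13:2, 0.0074 |
| 25 | 19:6 at 25-27; 20:5 at 28-50; 21:4 from 51 | 19:6, 0.0146; 20:5, 0.0041 |
| 50 | 34:16 at 50-54; 35:15 at 55-75 | 34:16, 0.0153; 35:15, 0.0066 |

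Examples of Fisher p: 13:2 of 19 per arm, 0.00063; 20:5 of 31 per arm, 0.00022; 35:15 of 62 per arm, 0.00045. At looks 1 and 2 the two tests share a boundary once enough patients are enrolled. At look 3 Fisher's boundary is lower for any enrolment up to 75 per arm.

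**Chance of a flag by look 3.** This is a simulation of 40,000 trials with blocks of 4, complete follow-up, and the patients enrolled at each look. Risks are set so that the overall mortality is m: the lower-risk arm has 2m/(1 + RR) and the other has RR times that. For m = 40% and RR = 2 this gives 27% and 53%.

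| Risk ratio | Mortality | Binomial | Fisher |
|---|---|---|---|
| 2 | 40% | 12.0% | 36.5% |
| 2 | 50% | 10.9% | 49.1% |
| 1.5 | 40% | 0.9% | 6.3% |
| 1.5 | 50% | 0.6% | 8.7% |
| 1 | 40-50% | 0.01-0.02% | 0.14-0.16% |

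In the extreme case where all 150 are enrolled before every look, the tests agree at looks 1 and 2. By look 3 the rates are 14.5-14.9% against 34.2-35.6% at risk ratio 2, and 1.7% against 5.9-6.0% at 1.5. With no true difference they are 0.08% against 0.15-0.16%.

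The binomial split is conservative here because mortality is high. It ignores survivors, whose numbers limit how unequal the split can become by chance. If deaths were rare relative to the numbers at risk, its false-flag rate over three looks would be about 0.24%.

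**The case against.** The strongest reply is that this text is only a proposal. Section 12 leaves the final rule to a charter drafted with the DSMB chair and lead statistician and approved before enrolment, and that charter may already differ. This stands: the finding concerns the wording in the protocol, not the conduct of the trial.

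Second, a sign test on the split of deaths is a legitimate exact test and suits looks triggered by death counts. This also stands, but it rescues only one of the two named options, and only if the text says so.

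Third, the caregiver wording fixes neither a test nor a threshold, T3 data exist, and the DSMB sees PHQ-9, GAD-7 and PTSS scores at every meeting. That limits the harm but does not supply T2 data. It is also fair that section 8 lists efficacy outcomes rather than a collection schedule, so the T2 point rests mainly on Appendix 5.

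Fourth, the size of the power gap depends on assumptions. The plan sets no power target for mortality, and a risk ratio of 2 is illustrative. The 40-50% figure comes from the length-of-stay discussion. If every death fell at day 90, Fisher's rate by look 3 at risk ratio 2 drops to 34-41%, with the binomial at 10-12%. The gap narrows but remains.

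**Conclusion.** The concern holds on both parts, as errors in provisional wording. PHQ-9 and PTSS cannot be examined at T2 under the current schedule. The signed-rank option is undefined for unpaired yes/no deaths, and the sign test is usable only as an unstated binomial split.

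Under 1:1 allocation, 40-50% three-month mortality and a doubled risk, that reading flags by the third look about one quarter to one third as often as Fisher's test (11-12% against 37-49%). At a risk ratio of 1.5 either test usually misses the difference.

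The consequence is modest. A flag only triggers closer examination. Deaths are reported to the DSMB chair within 72 hours (section 11), and the DSMB can request tests or act on a clinically significant rise in mortality or PHQ-9 (section 12). Efficacy conclusions are unaffected. The point is worth considering rather than critical.

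**What to change.** In section 12 and the DSMB charter:

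1. Reconcile the caregiver look with Appendix 5, so that it uses only time points at which PHQ-9 and PTSS are collected: T3, and T4 if intended.
2. Replace the sign and signed-rank wording with one pre-named, two-sided, unpaired comparison of deaths by arm, chosen with the DSMB statistician. Examples are Fisher's exact test among patients enrolled at the look, or a log-rank test. Keep the same looks and the 0.001 flag. If a binomial split of deaths was meant, say so explicitly.
3. Optionally, if a formal test of the distress scores is intended, name an independent-samples test such as the Wilcoxon rank-sum.

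The cost is wording in two documents. T3 and T4 scores and dates of death are already collected, so no extra data, patients or staff are needed.

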Appendix 1: Study Workflow

Protocol Version: 5.1 Dated: 13 June 2022 Page 34 of 42

Appendix 1: Study Workflow Continued

Protocol Version: 5.1 Dated: 13 June 2022 Page **35** of **42**

Appendix 2: Acute and Chronic Palliative Care Triggers

Phenotypes	Narrative description of 'positive' trigger	Time period relevant for screening by PCplanner	Data source in EHR
Acute phenotypes			
Mechanical ventilation	Mechanical ventilation delivered via either an endotracheal tube or tracheotomy for ≥24 hours	At any point during the first 48 hours of the current ICU admission	Respiratory care provider flowsheet
Shock	Defined as ANY use of ANY continuous intravenous vasopressor medication for ≥4 hours	At any point during the first 48 hours of the current ICU admission	Medication listNursing flowsheetVital signs flowsheet
Severe acute neurological injury	Acute intracranial hemorrhage Ischemic stroke Traumatic brain injury	At any point in current hospitalization until time of screening(i.e., 48 hours after ICU admission)	Physician billingProblem list
Cardiac arrest	Has cardiac arrest managed in ED or during hospitalization	At any point in current hospitalization (or preceding ED visit for out-of-hospital cardiac arrests)	Physician Billing
Multisystem organ failure that is worsening	Present if Sequential Organ Failure Assessment [SOFA] score on ICU day 2 (i.e., hours 25-48 after ICU admission) is greater than SOFA score on ICU day 1 (i.e., hours 0-24 after ICU admission)	ICU days 1 and 2 (i.e., comparing first 24 hours of ICU admission to second 24 hours of ICU admission)	LabMedicationsRespiratory care provider flowsheet
Acute renal failure	Use of continuous venovenous hemodiafiltration (CVVHD) for ≥1 hour during screening period	on EITHER ICU day 1 (i.e., within 24 hours of ICU admission) OR ICU day 2 (within 48 hours of ICU admission) *	 Medication list from nursing flowsheet Dialysis flowsheet Laboratory test

Protocol Version: 5.1 Dated: 13 June 2022 Page **36** of **42**

Chronic phenotypes			
Dementia	Alzheimer'sMulti-infarctOther dementia	 Present before hospitalization (i.e., Problem List) Present at any point in current hospitalization until time of screening (i.e., 48 hours after ICU admission) 	Physician billingProblem list
Admitted from facility	Admitted from Skilled Nursing Facility (SNF) or Long-Term Acute Care (LTAC) facility *	At any point in current hospitalization up until time of screening (i.e., 48 hours after ICU admission)	Intake flowsheet
Declining health trajectory	 ≥2 hospital admissions (includes Emergency Department visits) * ≥1 ICU admission 	Within the 3 months (or 90 days, whatever is easier) that preceded the date of the current hospital admission	Admission records
Declining functional status	≥2 activities of daily living (ADL) limitations *	At any point in current hospitalization	Nursing intake flowsheet
Advanced cancer	Cancer and/or metastatic cancer diagnosis	At any point in current hospitalization	Physician billingProblem list

[figure not shown]
Protocol Version: 5.1 Dated: 13 June 2022 Page **37** of **42**

Appendix 3: Schedule of Events

	Day 0 (In-Hospital, Baseline)	Family Meeting (Day 0, +3 days)	Day 4 (+4 days)	Family Meeting (Day 4, +3 days)	Day 8 (+4)	Day 90 (+28 days)
Screening	Х					
Consent (a)	Х					
App Registration	Х					
T1 Survey (b)	Х					
Randomization (c)	Х					
T2 Survey (d)			Х			
T3 Survey (d)					X	
T4 Survey (d)						Х
ICU Physician Family Meeting (e)		Х				
Palliative Care Family Meeting (f)				X		
Data Entry (g)	х		Х		Х	
AE/SAE assessment (h)	х		X		Х	Х
Survival Status (i)		Х				Х
End of Study		Х				Х

- a) Study team is only able to approach family members (LARs) for consent once the ICU physician has marked the patient "approved" in the PCplanner web application (or if the ICU attending has opted out of approval for all patient/family dads).
- b) Survey 1, T1 is to be completed ideally on the day of consent, but within 72 hours.
- c) Family members are eligible for randomization to the study based on their NEST score at the completion of survey 1, T1 (> 10). Family members can be randomized to either the intervention or the control arm.
- d) The timing of completion of surveys T2, T3, and T4 are directly linked to the timing of completion of survey 1, T1. Family members will receive automated alerts notifying them of survey completion at each set time interval based on the completion of T1.
- e) The ICU Physician Family meeting occurs for any family member that is randomized to the intervention arm. The ICU physician in attendance will receive automated alerts notifying them of patient/family enrollment, the NEST score and associated results and daily reminders to complete the family meeting.
- f) Like the ICU Physician family meeting, the Palliative Care family meeting will occur for those individuals who are randomized to the intervention arm; however, only family members who receive a NEST score > 25 or > their T1 NEST score at the completion of T2 will illicit the Palliative Care family meeting. The ICU Physician is responsible for facilitating in the coordination of the Palliative Care family meeting.
- g) Data entry is to be completed within the study EDC, REDCap.
- h) AE/SAE assessment and survival status will be completed via EMR review and/or telephone interview.

Appendix 4: Survey timelines and rules

T3 allowable window [contingent on T2 completion]; possible from study day 7 to study day 12
T3 will be available at 17:00 3 calendar days from time of T2 completion until 23:59 8 calendar days from time of T2 completion

Dated: 13 June 2022 Protocol Version: 5.1 Page 39 of 42

[figure not shown]

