Randomization will be stratified by three variables:

Protocol Version: 5.1 Dated: 13 June 2022 Page 8 of 42

- Department location at the time of ICU admission and informed consent (i.e., Medical versus Surgical)
- Palliative Care Trigger type (i.e., Acute versus Chronic; see Appendix 2)
- Baseline NEST score (i.e., ≥25 vs. <25 but ≥10)

All family members, regardless of their randomization arm will be asked to complete a total of four surveys, as listed below (see Appendix 3 for survey timeline):

- T1: to be completed within 72 hours of informed consent; study day 1
- T2: to be completed on study day 4
- T3: to be completed on study day 8
- T4: to be completed on study day 90

Surveys are completed remotely and electronically via the web application by the enrolled family member. Reminders are automatically provided by the PCplanner platform to the family members via email and/or text alerts to complete the surveys (Appendix 4).

Patients enrolled into this study, at the consent of their legally authorized representative (LAR), will passively participate in the study. Passive participation includes allowing the study team to access and abstract relevant clinical data from the patient's EMR. The clinical data abstracted for the purposes of this research project will be housed in the secure, EDC (REDCap).

Clinicians, whether ICU attending or Palliative Care, will be asked to complete a baseline survey at the time in which informed consent is obtained. The baseline survey will collect relevant information from the clinician, such as sociodemographic and professional information, as well a contact information (e.g., email address and cell phone number). Clinicians, who are assigned to an intervention family, will receive automatic text and/or email alerts via the web application informing them of the completed survey(s), reported needs, and the need to complete a family meeting.

Aim 3

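### Appendix 4 times the primary T3 survey from T2 and makes it depend on T2, while Appendix 3 times it from T1; T3 anchor, window and day count need one rule

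*Combined protocol and SAP*

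**What the plan says.** All references are to the combined protocol and SAP.

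- **Appendix 4** heads the T3 rule "T3 allowable window [contingent on T2 completion]; possible from study day 7 to study day 12" and adds "T3 will be available at 17:00 3 calendar days from time of T2 completion until 23:59 8 calendar days from time of T2 completion".
- **Appendix 3, note d**, uses another clock: "The timing of completion of surveys T2, T3, and T4 are directly linked to the timing of completion of survey 1, T1". The alerts follow it: "Family members will receive automated alerts notifying them of survey completion at each set time interval based on the completion of T1". The note sets no T2 condition. The column headings put T2 at day 4 and T3 at day 8, each with four further days.
- **Section 5, Study data collection**, also gives T3 as day 8 with up to four days. Its T2 entry is day 4 with four days counted from randomisation, which can be read as ending on day 4 or on day 8.
- **Section 3, Study Overview, Aim 2**: "All family members, regardless of their randomization arm will be asked to complete a total of four surveys". T1 is described as "T1: to be completed within 72 hours of informed consent; study day 1" and T3 as "T3: to be completed on study day 8". Appendix 3 labels the baseline column differently; its heading begins "Day 0 (In-Hospital, Baseline".
- **Section 5, participant statuses**: a randomised family member is required to do T2, T3 and T4, and at least 75% of the surveys is enough for completed status.
- **Section 3, Primary Outcomes**, makes NEST at T3, eight days after randomisation, the primary outcome. **Appendix 5** collects NEST at T1, T2 and T3 only.
- **Section 11** expects surveys to be late or missed and does not treat either as a deviation.

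**The concern.** Two printed rules govern when the primary endpoint is collected, and they give different answers. For a caregiver who does T2 late, the two windows overlap only in part. For a caregiver who misses T2, Appendix 3 still offers T3, while the Appendix 4 rule has no date to count from. That caregiver would have a baseline NEST and nothing after randomisation.

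Section 8 plans a mixed model in SAS PROC MIXED for NEST over time. Such a model can use incomplete records under a missing-at-random assumption, but a record with only a baseline value says little about the difference between arms at T3. T2 completion is also a post-randomisation event: in the intervention arm it is meant to follow the ICU family meeting. Making T3 depend on it could let missingness differ between arms. The supplementary missing-data analysis in section 8 is written for T4, not T3.

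**Working it through.** **1. Reproduce the Appendix 4 window.** The rule is: opening day = T2 day + 3, closing day = T2 day + 8. With T2 on its nominal day 4 this gives 4 + 3 = 7 and 4 + 8 = 12, which is the stated range.

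**2. Apply the same rule to the other T2 days that Appendix 3 allows (days 4 to 8),** and compare with the T3 window of days 8 to 12 in Appendix 3 and section 5.

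| T2 done on day | T3 window under Appendix 4 rule | Days shared with 8–12 |
|---|---|---|
| 4 | 7–12 | 5 of 6 |
| 5 | 8–13 | 5 of 6 |
| 6 | 9–14 | 4 of 6 |
| 7 | 10–15 | 3 of 6 |
| 8 | 11–16 | 2 of 6 |

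Over the full T2 window the rule spans days 7 to 16, so the stated 7 to 12 holds only for T2 on day 4. If day 12 is meant as a cap, a caregiver who does T2 on day 8 has only days 11 and 12 for T3. Appendix 4 as printed does not say which is meant.

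**3. Test whether the day count explains the difference.** If T1 is day 1, day 8 falls 8 − 1 = 7 days later; if T1 is day 0, it falls 8 days later. Moving every day by one cannot turn 7–12 into 8–12, because the opening days differ while both windows close on day 12. The numbering is a separate discrepancy.

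**4. Follow a caregiver who misses T2.**

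| Source | Is T3 offered? |
|---|---|
| Appendix 3, note d | Yes, on the T1 clock |
| Section 3, Aim 2 | Yes, four surveys asked of all |
| Section 5, randomised status | Yes, T3 required |
| Section 5, completed status | Consistent with yes: T1, T3 and T4 are 3/4 = 75% |
| Appendix 4, printed text | No opening date can be computed |

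**5. Check whether a power loss follows.** Inputs from section 8: difference 8.80, SD 21.1, correlation 0.64, 150 randomised, 10% dropout by day 8. A two-sided 5% test is assumed.

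- SD of change = 21.1 × √(2 × (1 − 0.64)) = 17.90.
- With 65 per arm, the normal approximation gives 80.0% power, matching the plan.
- After the planned dropout, 150 × 0.9 = 135 remain and power is 81.5%.

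If caregivers without T3 because of a missed T2 already fall within that 10%, there is no shortfall. The documents give no T2 miss rate, so a loss beyond this cannot be calculated.

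**The case against.** The tempting stronger reading is that a missed T2 forfeits the primary outcome and leaves the trial underpowered. The documents do not support it, for four reasons.

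- Section 5 says that Appendix 4 shows the survey time frames, yet only two lines about T3 can be read and the figure is not shown. A rule for a missed T2 may be there.
- The words about T2 may mean only that the T3 dates depend on T2. No readable sentence says that T3 is withheld, and sections 3 and 5 and Appendix 3 point to T3 for everyone.
- With no T2 miss rate, any power loss is conjecture. Some caregivers who skip T2 would skip T3 under any rule, and the planned 10% may already include them.
- Section 5's T2 entry can be read as ending on day 4, in which case 7 to 12 is exact.

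A further argument is that spacing T3 from T2 looks deliberate. Appendix 3 allows three days after day 4 for the palliative care meeting, and section 5 places that meeting before T3.

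These points remove the power argument and leave the missed-T2 consequence unproven. They do not remove the conflict. The T2 anchor contradicts note d whatever the figure shows, and ending T2 on day 4 would contradict Appendix 3's own T2 window. Even on the mild reading, the printed rule needs a T2 date to open T3.

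**Conclusion.** The conflict in the printed text stands: two anchors for T3 (T1 and T2), stated windows of 7–12 and 8–12, an Appendix 4 rule that reaches day 16 if T2 may be done on day 8, and two baseline day numbers. It should be fixed, because it concerns collection of the primary endpoint in a trial that expects missed surveys.

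Confidence is medium. The day-16 figure rests on Appendix 3's T2 window. The missed-T2 consequence rests on the readable part of Appendix 4 being the whole rule, which cannot be confirmed. No loss of power is claimed.

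**What to change.** State in Appendix 4 that T3 is offered to every randomised caregiver whether or not T2 was completed. When T2 is missed, T3 should open on the T1/randomisation clock; spacing from T2 can stay when T2 is done. If the figure already contains such a rule, repeat it in the text.

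Then reconcile section 3 (Aim 2), section 5 (Study data collection), Appendix 3 and Appendix 4 on:

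- the T3 anchor;
- the opening and closing days, and whether day 12 is a cap;
- the last allowable day for T2;
- whether baseline is day 0 or day 1;
- how the T3 window sits relative to the T2-triggered meeting that section 5 places before T3.

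A prespecified sensitivity analysis for missing T3 NEST would be a useful option.

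The cost is a small app scheduling change and a short amendment, plus one analysis if the option is taken. Some T3 responses will come from caregivers with no T2 and, in the intervention arm, no T2-triggered meeting.
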